### **3.2. Clarification of Hierarchical Testing Strategy**

Section 8.4 of the SAP specifies that all endpoints tested at Year 1 and Year 2 will use a significance level of 0.025. Within each year, endpoints are tested following a fixed-sequence hierarchical testing strategy. The total significance level (0.05) was split between Year 1 and Year 2 as a strategy to reserve alpha to test Year 2 if the Year 1 testing sequence was not statistically significant. Formal testing in the sequence may proceed so long as statistically significant evidence of benefit continues to be shown. If in the sequence one endpoint does not show statistically significant evidence of benefit, formal statistical testing of subsequent endpoints will not occur.

As a clarification to the SAP, if there is a significant treatment effect for both Year 1 endpoints, then the significance level for Year 1 (0.025) remains available to be carried forward (recycled or passed along) to the Year 2 testing sequence. Thus, if both Year 1 endpoints are significant, the Year 2 testing sequence will be tested using a significance level of 0.05. This approach aligns with the fixed-sequence method in FDA guidance (Multiple Endpoints in Clinical Trials., January 2017).

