#### 4.3.1. Primary Endpoints

With 157 patients enrolled (78 in one group and 79 in the second group), the study will have approximately 80% power to detect a difference between the two treatment groups in change from baseline in eGFR of 3.4 mL/min/1.73 m^2 for the primary endpoint at Week 48 in Year 1. The power calculation for Year 1, which was based on mixed-model repeated measures (MMRM) analysis, assumes the following:

- 9 repeated measurements (Weeks 1, 2, 4, 6, 8, 12, 24, 36, and 48) having compound symmetry covariance structure
- The correlation between observations on the same subject is 0.7
- Two-sided Type I error rate of 0.025
- Standard deviation of change from baseline in eGFR of 8 mL/min/1.73 m^2
- Analyses at Week 48 are based on the intent-to-treat (ITT) population

Analysis of the Year 2 primary endpoint, which also will use the ITT population, will have approximately 80% power to detect a difference of 3.3 mL/min/1.73 m^2 assuming 13 repeated measurements, a correlation of 0.7 between observations, a standard deviation of 8 mL/min/1.73 m^2, and a two-sided type I error rate of 0.025. The primary analysis of efficacy will use an unstructured covariance structure, which is expected to have approximately the same power as the analysis with compound symmetry used for study planning.

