#### 4.3.2. Key Secondary Endpoint

With 157 patients enrolled, the study will have a minimum detectable difference (i.e., 50% power) between the two treatment groups in change from baseline in eGFR of approximately 2.9 mL/min/1.73 m^2, and 80% power to detect a difference of 4.0 mL/min/1.73 m^2 for the key secondary endpoint at Year 1 and at Year 2. The power calculation, which was based on a 2-sample t-test as an estimate for the planned ANCOVA analysis, assumes the following:

- Two-sided Type I error rate of 0.025 for Year 1 and 0.025 for Year 2
- Standard deviation of change from baseline in eGFR of 8 mL/min/1.73 m^2
- Multiple imputation is used for missing data
- Analyses of the key secondary endpoint are based on the ITT population

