#### **8.4. Multiple Comparisons and Multiplicity**

The trial includes separate Phase 2 and Phase 3 cohorts, where the cohorts constitute independent sets of patients. Therefore, the Phase 2 analysis has no impact on the Type I error rate for the Phase 3 analysis.

The Phase 3 cohort includes a family of hypothesis tests following the first year of treatment and a second family of hypothesis tests following the second year of treatment. All endpoints tested at Year 1 will use a significance level of 0.025 and those tested at Year 2 will also use a significance level of 0.025. Within each year, endpoints are tested following a fixed-sequence hierarchical testing strategy. Formal testing in the sequence may proceed so long as statistically significant evidence of benefit continues to be shown. At such point in the sequence that one endpoint does not show statistically significant evidence of benefit, formal statistical testing of subsequent endpoints will not occur.

Testing endpoints in the following sequence protects the overall type I error rate of 0.05 for the study:

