4. Compound symmetry covariance structure (assuming equal correlation for measurements from a patient, regardless of how far apart in time they were taken). A compound symmetry covariance structure was assumed in the sample size calculation.

The difference between bardoxolone methyl and placebo in change from baseline of eGFR is estimated along with the 95% confidence interval at Week 48 for the primary analysis of the Year 1 primary endpoint.

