### **8.7. Year 1: Key Secondary Endpoint**

#### **8.7.1. Primary Analysis of Year 1 Key Secondary Endpoint**

The Year 1 key secondary endpoint of this study is the change in eGFR at Week 52 (i.e., 4 weeks following the last dose after one year of drug exposure). Analysis of Week 52 assesses the preserved drug benefit (relative to placebo) following withdrawal of treatment; therefore, analysis of Week 52 data does not include the eGFR values collected during treatment.

The change from baseline eGFR at Week 52 for patients treated with bardoxolone methyl is compared to placebo using an analysis of covariance (ANCOVA) model, with BASE\_eGFR,

ACR\_STRAT, and TRT\_EXP1 as covariates, and TRT as the fixed effect. Inclusion of the fraction of expected one-year exposure to treatment (TRT\_EXP1; Section 6.5.11) in the ANCOVA model as a covariate provides an adjustment for eGFR values collected from early discontinuation patients having follow-up collected after less than 1-year of drug exposure.

The ANCOVA analysis uses eGFR values collected in the Week 52 analysis window (Section 6.5.4), which includes the follow-up assessment for patients who discontinued treatment early in the first year. Missing Week 52 eGFR data are imputed as defined in Section 8.5.3 using standard imputation.

The difference between bardoxolone methyl and placebo in change from baseline of eGFR is estimated along with the 95% confidence interval at Week 52.

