## **8.9. Year 2: Key Secondary Endpoint**

### **8.9.1. Primary Analysis of the Year 2 Key Secondary Endpoint**

The Year 2 key secondary endpoint of this study is the change in eGFR at Week 104 (i.e., 4-weeks following the last dose after two years of drug exposure). Analysis of Week 104 assesses for retained drug benefit (relative to placebo) following withdrawal of treatment; therefore, the analysis of Week 104 data does not include eGFR values collected during treatment.

The change from baseline eGFR at Week 104 for patients treated with bardoxolone methyl are compared with placebo in a manner similar to the ANCOVA analysis of Week 52 in Year 1 (Section 8.7.1) with the following modification:

- TRT\_EXP2 is added as a covariate and TRT\_EXP1 is removed

The analysis uses eGFR values collected in the Week 104 analysis window (Section 6.5.4), which includes the follow-up assessment for patients who discontinued treatment early in the second year. Discontinuing treatment in the second year requires that patients received at least one dose of study drug in the second year. Missing Week 104 eGFR data are imputed as described in Section 8.5.3.

The difference between bardoxolone methyl and placebo in change from baseline of eGFR are estimated along with the 95% confidence interval at Week 104.

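### Weeks 48 and 52 are tested at two-sided 0.025 but reported with 95% intervals; Year 2 has the same mismatch only if the Year 1 alpha is not carried forward

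*SAP*

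**What the plan says.** **Test level.** SAP Section 8.4 states: "All endpoints tested at Year 1 will use a significance level of 0.025". For the second year it sets the same level: endpoints at Weeks 100 and 104 are also tested at 0.025. Section 4.3.1 gives the primary endpoint a "Two-sided Type I error rate of 0.025", and Section 4.3.2 gives the key secondary endpoint a "Two-sided Type I error rate of 0.025 for Year 1 and 0.025 for Year 2". Section 8.2 states a two-sided alternative. The DMC rule in Section 5.1 and the tipping-point analyses in Sections 8.6.2.1 and 8.7.2.1 also use 0.025. Section 6.1 limits the general 0.05 convention to endpoints that Section 8.4 does not cover.

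**Carry-forward.** Section 3.2 of the SAP addendum adds that "if both Year 1 endpoints are significant, the Year 2 testing sequence will be tested using a significance level of 0.05".

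**Interval level.** The treatment difference "is estimated along with the 95% confidence interval at Week 48" (8.6.1), "is estimated along with the 95% confidence interval at Week 52" (8.7.1), and at Week 104 the estimates "are estimated along with the 95% confidence interval at Week 104" (8.9.1). Section 8.8.1, on Week 100, names no interval level; it refers back to the model in 8.6.1. We found no 97.5% interval in the documents, and no statement that the 95% intervals are descriptive.

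**The concern.** A two-sided test at level alpha rejects exactly when the interval at confidence 1 minus alpha excludes zero, provided both use the same estimate, standard error and reference distribution. For a test at 0.025 that interval is 97.5%. A 95% interval is narrower, so there is a band of results in which it lies wholly above zero although the endpoint has failed.

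The stake is how the main efficacy tables are read. The alpha was split to keep a second chance at Year 2 if Year 1 did not succeed. In that case nothing is carried forward, Year 2 stays at 0.025, and the 95% level matches the test in neither year. Section 2.1 describes the off-treatment change as the trial's main analytic purpose, so the Week 52 and Week 104 intervals will be read closely. Sensitivity results also go into forest plots, where readers commonly judge significance by whether the interval crosses zero.

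**Working it through.** **Level of test against level of interval**

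| Endpoint | Test level (two-sided) | Stated interval | Matching interval |
|---|---|---|---|
| Week 48 | 0.025 | 95% | 97.5% |
| Week 52 | 0.025 | 95% | 97.5% |
| Week 100, alpha not carried forward | 0.025 | none stated | 97.5% |
| Week 104, alpha not carried forward | 0.025 | 95% | 97.5% |
| Week 100, alpha carried forward | 0.05 | none stated | 95% |
| Week 104, alpha carried forward | 0.05 | 95% | 95% |

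**Step 1: reproduce the plan's figures, to settle whether 0.025 is two-sided.** Section 4.3.2 gives a two-sample t-test with SD 8. Section 4.3.1 gives 78 and 79 patients.

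- SE = 8 × √(1/78 + 1/79) = 1.277, with 155 degrees of freedom.
- Two-sided 0.025: t(0.9875, 155) = 2.263. The minimum detectable difference is 2.263 × 1.277 = 2.89 (stated: about 2.9). Power at 4.0, from the noncentral t, is 80.7% (stated: 80%).
- Two-sided 0.05, which has the same upper critical value as one-sided 0.025: t(0.975, 155) = 1.975. The minimum detectable difference is 1.975 × 1.277 = 2.52, and power at 4.0 is 87.6%.

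Of these readings, only two-sided 0.025 fits the stated figures.

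**Step 2: the band of disagreement for the key secondary endpoint.** The 95% half-width is 2.52 and the 97.5% half-width is 2.89. An observed benefit between these values has 0.025 < p < 0.05: it fails the test, but its 95% interval excludes zero. For example, an observed difference of 2.7 gives t = 2.7/1.277 = 2.11 and p = 0.036. The 95% interval is 0.18 to 5.22; the 97.5% interval is −0.19 to 5.59.

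**Step 3: how often this happens.** The probability of landing in the band in favour of drug is the power at 0.05 minus the power at 0.025.

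- True difference 4.0: 0.876 − 0.807 = 0.069.
- True difference 2.9: 0.617 − 0.504 ≈ 0.112.
- True difference 0: 1.25% in favour of drug, 2.5% counting both directions.

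These are probabilities for one endpoint that is tested at 0.025. For a Year 2 endpoint tested at 0.05 the disagreement probability is zero.

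**Step 4: the primary endpoints.** Section 4.3.1 assumes compound symmetry with correlation 0.7 over k visits. Taking the variance as SE² × (1 + (k − 1) × 0.7)/k comes close to the stated power.

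- Year 1, k = 9: SE = 1.277 × √(6.6/9) = 1.094. Power at 3.4 is 80.7%. The band is 1.960 × 1.094 to 2.241 × 1.094, or 2.14 to 2.45, with probability 6.8% at 3.4.
- Year 2, k = 13, if tested at 0.025: SE = 1.277 × √(9.4/13) = 1.086. Power at 3.3 is 78.7%. The band is 2.13 to 2.43, with probability 7.2% at 3.3.

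This variance averages over visits, so the bands are indicative only. The standard error of a contrast at one visit may be larger.

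**Step 5: width.** The ratio of normal multipliers is 2.241/1.960 = 1.144, so the matched interval is about 14% wider.

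**The case against.** The strongest reply is that no decision uses the interval. Every significance rule in the SAP is a p-value rule, and the 95% interval is valid for what it claims to be. This stands. A reader might infer that the 95% level inflates type I error or undermines the multiplicity control; the documents do not support that, because the tests, their levels and the power calculations are untouched.

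Second, a reader might infer that all four endpoints are mismatched whatever happens. They are not. If both Year 1 endpoints reach p < 0.025, their 95% and 97.5% intervals all exclude zero, so no contradiction can appear. Year 2 is then tested at 0.05, where 95% is the matched level. Under Section 5.1 the sponsor unblinds and reports Year 1 early only in this case. A contradiction can therefore arise only when Year 1 is not fully successful, and it would then appear in the final report.

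Third, Section 8.8.1 does not state a 95% interval. The sentence in 8.6.1 is written for Week 48, so for Week 100 the level is inferred.

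Fourth, a matched level does not remove every misleading interval. If Week 48 fails, Week 52 is not formally tested, yet its 97.5% interval may still exclude zero. The same holds for Week 104 after Week 100. This also stands, and the fix has to cover it.

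These replies narrow the point. They do not explain why the stated interval level can contradict the stated decision rule in the scenario for which the alpha was split.

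**Conclusion.** The mismatch is real for Weeks 48 and 52. It applies to Week 104, and to Week 100 if the 8.6.1 reporting is inherited, only when the Year 1 alpha is not carried forward. It is a minor defect of reporting and interpretation. Its size is an observed key secondary difference of 2.52 to 2.89 mL/min/1.73 m², with probability about 7% at a true difference of 4.0 and 11% at 2.9.

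These figures assume the SAP's planning SD of 8, complete data on 157 patients and a two-sample t-test. The planned ANCOVA with multiple imputation will have a different standard error, so the band will move, but it will exist whenever a test at 0.025 is shown beside a 95% interval. Section 3.2 of the addendum does set the Year 2 test level for each Year 1 outcome; what is missing is a sentence that ties the interval level to it.

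**What to change.** - In Sections 8.6.1 and 8.7.1, report 97.5% intervals for Weeks 48 and 52.
- In Sections 8.8.1 and 8.9.1, state the interval level as 1 minus the operative alpha: 97.5% if Year 2 is tested at 0.025, and 95% if it is tested at 0.05. This also supplies the level that 8.8.1 lacks.
- Where a 95% interval is kept beside a 97.5% one, label it descriptive.
- Label the interval for any endpoint that the fixed sequence does not reach as descriptive, whatever its level.

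The cost is a few sentences in the SAP, one extra table column and intervals about 14% wider where 97.5% applies. No new data, models or tests are needed.

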### **8.6.2. Sensitivity Analyses**

Sensitivity analyses are included to assess the robustness of conclusions to the primary analysis of the Year 1 primary efficacy endpoint (i.e., change in eGFR at Week 48), and to assess the assumption of MAR. The following sets of sensitivity analyses will be summarized in tables and forest plots: tipping point with multiple imputation, control-based imputation, MMRM fit to the as-treated population, and MMRM fit to the per protocol population. Additional sensitivity analyses may be performed as appropriate.

#### **8.6.2.1. Tipping Point**

The following tipping point sensitivity analysis is performed to assess how severe departures from MAR must be in order to overturn conclusions from the primary analysis:

1. The PROC MI procedure in SAS is used to generate 100 datasets satisfying the assumption of monotone missingness, imputing any missing eGFR values using multiple imputation. Imputation is based on the non-missing observations within each treatment group.

2. The PROC MI procedure in SAS is applied to each of the 100 datasets subsetted to the placebo group and all missing values in the placebo group are imputed. These 100 datasets will then be used for the tipping point analysis.
3. For the tipping point analysis with a shift parameter, patients in the bardoxolone methyl group with a missing value will be multiply imputed separately from the placebo-treatment arm and are assigned a shift parameter in the imputation procedure for progressively worse (lower) scores to find the point at which statistical significance is lost. Specifically, if the outcome of the hypothesis test favors bardoxolone methyl over the placebo group ( $p$ -value  $< 0.025$ ), then one point is subtracted as a shift parameter in the imputation for the bardoxolone methyl group, while keeping the data for the placebo group unchanged.
4. A mixed model repeated measures (MMRM) model (see Section 8.6.1) is used to analyze each of the 100 completed data sets. PROC MIANALYZE is used to combine these results to obtain the final estimates for the given value of the shift parameter.
5. This “eGFR shifting”, as outlined in steps 3 and 4, is repeated with one shift point at a time until the hypothesis test no longer rejects the null hypothesis in favor of the bardoxolone methyl group over the placebo group (i.e., when the  $p$ -value becomes greater than 0.025). Additional increments may be used to locate the tipping point. If the result is not quite statistically significant, progressively higher scores are added to find the point at which statistical significance is attained.

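### If Year 2 is tested at 0.05, the tipping-point steps still start and stop at p = 0.025 and no longer match the test whose conclusion they are meant to stress

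*SAP*

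**What the plan says.** SAP 8.4 sets 0.025 for each year; of the second-year endpoints it says that "those tested at Year 2 will also use a significance level of 0.025". SAP addendum 3.2 changes this in one scenario: "if both Year 1 endpoints are significant, the Year 2 testing sequence will be tested using a significance level of 0.05".

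The tipping-point steps are written out under Year 1, in 8.6.2.1 for Week 48:

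- Step 3: if the test favours bardoxolone methyl with p < 0.025, "one point is subtracted as a shift parameter in the imputation for the bardoxolone methyl group".
- Step 5: the shift is repeated one point at a time until the p-value "becomes greater than 0.025".
- Step 5, other branch: "If the result is not quite statistically significant, progressively higher scores are added" until significance is reached. No number is attached to this branch.

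Section 8.7.2.1 gives the same thresholds and branches for Week 52. Sections 8.8.2 and 8.9.2 carry the procedures to Weeks 100 and 104 and restate no threshold. Nothing in the addendum mentions the tipping-point analysis.

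**The concern.** The stated aim of the tipping point is to find how far the missing-at-random assumption must fail before the primary conclusion changes. Its threshold therefore has to be the level at which that conclusion was drawn. Once the Year 1 alpha is carried forward, that level is 0.05 for Year 2, while the steps still say 0.025.

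The analysis carries some weight. SAP 12.2 relies on it, together with control-based imputation, to check the missing-at-random assumption after dropping the protocol's Jump to Reference imputation for Week 48. Missing data are also a live matter in Year 2: the protocol addendum (new 15.6.1) records data that cannot be assessed remotely as missing, and SAP addendum 4.5 leaves out efficacy data collected after a COVID-19 adverse event.

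**Working it through.** **Inputs.** 78 and 79 patients (SAP 4.3.1); SD 8 (4.3.1, 4.3.2); correlation 0.7 and, for Year 2, 13 repeated measurements (4.3.1); "Two-sided Type I error rate of 0.025 for Year 1 and 0.025 for Year 2" (4.3.2); Year 2 level of 0.05 after Year 1 success (addendum 3.2).

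**1. The plan's own figures.** SE = 8 × √(1/78 + 1/79) = 1.277. For the two-sample t-test with 155 df at two-sided 0.025, the critical difference (50% power) is 2.263 × 1.277 = 2.89, against 2.9 in 4.3.2. Power at 4.0 is 80.7%, against 80%. For Week 100 under compound symmetry, SE = 1.277 × √((1 + 12 × 0.7)/13) = 1.086, and power at 3.3 is Φ(3.3/1.086 − 2.241) = 78.7%, against approximately 80%. The figures reproduce.

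**2. The band that the steps miss.** At 0.05 the Week 104 critical difference is 1.975 × 1.277 = 2.52. Differences between 2.52 and 2.89 mL/min/1.73 m² are significant at 0.05 but fail the p < 0.025 entry condition.

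**3. Chance of landing in the band** (normal approximation): Φ(d/SE − 1.960) − Φ(d/SE − 2.241).

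| Endpoint, true difference d | d/SE | Result |
|---|---|---|
| Week 104, 4.0 | 3.132 | 0.8795 − 0.8135 = 6.6% |
| Week 104, 2.9 | 2.271 | 0.6221 − 0.5118 = 11.0% |
| Week 100, 3.3 | 3.039 | 0.8597 − 0.7875 = 7.2% |

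In general terms, exactly 80% power at 0.025 gives Φ(3.083 − 1.960) − Φ(3.083 − 2.241) = 0.069, and 50% power gives Φ(2.241 − 1.960) − 0.5 = 0.111.

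**4. Effect on the reported shift.** If a share f of the bardoxolone methyl arm is missing and the SE is held fixed, the shift that brings the result to level α is (z_p − z_α) × SE / f. The documents give no missing rate, so f is assumed: 10%, with 5% and 20% as the range. For Week 104:

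- p = 0.03 (difference about 2.77). At 0.05: (2.170 − 1.960) × 1.277 / 0.10 = 2.7 points downward (5.4 at f = 5%, 1.3 at 20%). At 0.025: (2.170 − 2.241) × 1.277 / 0.10 = −0.9. No downward tipping point exists at that threshold; only an upward shift of 0.9 points would reach it (1.8 and 0.5).
- p = 0.01 (difference about 3.29). At 0.025: (2.576 − 2.241) × 1.277 / 0.10 = 4.3 points (8.5 and 2.1). At 0.05: (2.576 − 1.960) × 1.277 / 0.10 = 7.9 points (15.7 and 3.9). The direction is right, but the procedure stops early.

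**The case against.** The best defence is that 0.025 stands in Year 1 text, where it is always correct, and that Year 2 borrows the steps by cross-reference. The borrowing cannot be word for word anyway: step 4 points to the Week 48 model, so a reader must already substitute the Year 2 covariate and visits, and could substitute the Year 2 level too. The purpose and the stopping rule are also put in functional terms, with the number as a gloss on non-rejection. This shows what was probably meant. It does not remove an explicit number from both the entry and the stopping condition, and someone programming from the SAP could well code 0.025. The separate programming document is not available here, so what was coded is unknown.

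A reader might infer that a Year 2 p of 0.03 is sent the wrong way, into favourable shifts. The text does not establish that. The upward branch depends on the result falling short of significance and names no level, and 0.03 tested at 0.05 does not fall short. Read strictly, the result fits neither branch. Only if 0.025 is read into the upward branch does the shift go upward.

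It also stands that stopping at 0.025 when p < 0.025 makes a positive result look less robust than it is, so it cannot hide fragility. The SAP further allows additional sensitivity analyses (8.6.2, 8.7.2).

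**Conclusion.** The tipping-point steps are wrong as written for Year 2 in one scenario, and the severity is low. The defect arises only if both Year 1 endpoints are significant; otherwise 0.025 is the right threshold. In that scenario a result with p between 0.025 and 0.05 is declared significant with no clear instruction to stress it, and for p < 0.025 the tipping shift is understated, conservatively.

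The figures of about 7% and 11% are marginal chances per endpoint at the planning effects. They should not be read as the chance that the problem occurs. That also needs both Year 1 endpoints to succeed and, for Week 104, Week 100 to succeed first. SAP 4.3 says the two years are not independent, so the joint chance cannot be computed from the documents; at the stated effects it cannot exceed the marginal figures. The illustrative shifts rest on an assumed missing share and a fixed SE.

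Nor does the mismatch call the Year 2 tests into question. Type I error, the primary tests, and the control-based, as-treated and per-protocol analyses do not use this threshold.

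**What to change.** In SAP 8.6.2.1 and 8.7.2.1, replace each 0.025 with the significance level at which the endpoint was tested: 0.025 for Year 1; for Year 2, 0.025, or 0.05 if the Year 1 alpha is carried forward under addendum 3.2. Tie the upward-shift branch to the same level, so that every p-value falls into exactly one branch. The same sentence could be added once to the addendum, to govern 8.8.2 and 8.9.2. The cost is a wording change and one parameter in the program; no new data are needed. Made before the Year 2 database lock, it also removes a choice that would otherwise be made after the result is known.
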